### Extended Statistical Analysis Plan

Baseline characteristics between participants enrolled in the study and those screened but not enrolled, and between those enrolled during the control period and those enrolled during the intervention period, will be compared using chi-square tests and t-tests.

**Reach** is defined as the proportion of the target population who participate in the intervention. We will assess reach by calculating the percentage of patients and caregivers who received the pamphlet and video decision aids out of the total number of patients and caregivers enrolled in the intervention period.

**Effectiveness** of the intervention will be assessed through the primary outcome of decision quality: the extent to which medical decision making reflects the considered preferences of a well-informed patient. As such, co-primary endpoints were chosen comprising the two main International Patient Decision Aid Standards domains of decision quality—knowledge and values-choice concordance.

**Knowledge:** A 10-item knowledge test was developed by the study team and validated by clinicians and patients. Consistent with methods of Sepucha et al., the study team created a list of knowledge items based on clinical needs, local post-LVAD education standards, and needs assessment work with patients. We then surveyed patients, caregivers, MCS coordinators, and physicians to narrow the list and determine the key knowledge items and assure content validity. The acceptability of this measure was further assessed with patients and caregivers in a pilot of the trial protocol. Improvement in knowledge from baseline 1 (enrollment) survey to baseline 2 (post-education) survey was a co-primary endpoint.

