To assess the change in patient DT LVAD knowledge over time, we will fit a linear mixed model proposed for the analysis of stepped wedge designs. This model accounts for the repeated measures within subject, included a random effect for site and fixed effect indicators of intervention group and stepped wedge time period. This model adjusts for trends over time, assuming that changes occur similarly across all sites. We will assess any differences in baseline covariate distribution by intervention group, and will include covariates that are imbalanced by group in this linear mixed model. We will evaluate whether the change in knowledge score (percent correct) between baseline 1 and baseline 2 was different between the control and intervention groups.

**Values-Choice Concordance:** A values scale was also developed, modeled after a well-accepted values evaluation tool. During previous needs assessment work, one value rose above all others in considering DT LVAD: maximizing chances of survival with aggressive medical care versus not. We developed a single-item, 10-tier Likert values measure using the dichotomy of “Do everything I can to live longer, even if that means having major surgery and being dependent on a machine” (score 1) versus “Live with whatever time I have left, without going through major surgery or being dependent on a machine” (score 10). For caregivers, this read as “Do everything my loved one can to live longer, even if that means having major surgery and being dependent on a machine” (score 1) versus “Have my loved one live with whatever time he/she has left, without going through major surgery or being dependent on a machine” (score 10). At 1 month post-enrollment, we will create a dichotomous variable of whether the patient wanted to get the LVAD or did not want to get the LVAD (DT LVAD or medical management without LVAD), and patients and caregivers will report the patient’s treatment choice. Concordance between 1-month value score and patient/caregiver-reported treatment choice at 1-month is the other co-primary endpoint. Secondary outcome of concordance between 1-month value score and actual treatment received by 6-months will also be assessed. Actual treatment received by 6

months is recorded on the patient's medical record review and is defined as whether the patient had been implanted with the LVAD by 6 months or not implanted.

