To assess values-choice concordance, we will calculate the Kendall's tau correlation coefficient between the stated values score at 1 month and each of the treatment outcomes (patient/caregiver-reported treatment choice at 1 month, actual treatment received at 6 months), and look at the difference in this correlation coefficient by intervention group. To generate a confidence interval for this difference, we will perform 500 bootstrap samples and calculate the 2.5 and 97.5th percentiles.

**Secondary outcomes** measures include the following for both patients and caregivers:

- **Acceptability:** We will measure acceptability of education materials by using a modified version of decision aid acceptability developed by Barry et al.
- **Decision Conflict:** We will use the validated 15-item decision conflict measure developed by O'Connor et al.
- **Decision Regret:** We will use the validated 5-item decision regret scale.
- **Patient Health Questionnaire-2:** To assess depression in patients and caregivers at baseline and after their decision.
- **Perceived Stress Scale:** To assess the stress patients and caregivers feel during the decision making process.

And the following for patients only:

- **Control Preferences Scale (preferred and actual):** We will measure the participants' preferred role in decision making using the validated Control Preferences Scale and their actual control participation.
- **PEACE Illness Acceptance Measure:** For patients, we will assess patients' acceptance of their current heart failure illness and whether that impacts their decision to accept or decline DT LVAD.
- **Quality of Life (EQ Visual Analogue Scale):** For patients, we will assess their self-reported quality of life score through only the Visual Analogue Scale portion of the EQ5D, both pre and post decision.

And for caregivers only:

- **The Preparedness for Caregiving Scale:** For caregivers, we will assess their level of preparedness, both mentally and physically, pre and post decision.
- **Family Satisfaction with Care:** For caregivers, we will assess their satisfaction with the decision making process and their involvement.

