Secondary outcomes data will be scored and summarized according to the methods previously validated and published for each measure. Significance for differences by intervention group at specified time points for the categorical outcome scales will be determined using Chi-square tests. Differences in the continuous outcome scales by intervention group will be assessed via the linear mixed model described previously.

Missing data will be characterized at each time point. Analysis will account for missing data and will relax the missing data assumptions to missing at random conditional on observed data.

**Adoption** is defined as the absolute number, proportion, and representativeness of settings who are willing to initiate a program. We will calculate the total number of programs in the study who used the intervention at their program.

**Implementation** is defined as the extent to which the intervention is implemented as intended. Decision aid use will be reported by the study team with a checklist for each patient enrolled. We will calculate the percentage of patients who received the pamphlet and the video decision aids in certain ways (e.g. percent who received the decision aids from clinical personnel, percent who viewed the video in a clinical setting).

**Maintenance** will be assessed primarily by calculating the total number sites that decide at the conclusion of the study to maintain, modify, or discontinue the use of the decision aids.

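### The concordance co-primary compares one Kendall's tau per group with no period adjustment, although the SAP adjusts the knowledge co-primary for calendar trend

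*SAP*

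**What the plan says.** All references are to the SAP, Extended Statistical Analysis Plan.

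- **Co-primary status** (Values-Choice Concordance paragraph): "Concordance between 1-month value score and patient/caregiver-reported treatment choice at 1-month is the other co-primary endpoint". Choice is binary: "we will create a dichotomous variable of whether the patient wanted to get the LVAD or did not want to get the LVAD".
- **Concordance analysis** (paragraph after it): Kendall's tau between the 1-month values score and choice, after which the analysts will "look at the difference in this correlation coefficient by intervention group". The interval is a percentile interval from 500 bootstrap samples. No period term, site term, stratification or covariate is named. The same sentence covers 6-month concordance, a secondary outcome.
- **Knowledge analysis**: "we will fit a linear mixed model proposed for the analysis of stepped wedge designs". The model "included a random effect for site and fixed effect indicators of intervention group and stepped wedge time period", and the reason is given: "This model adjusts for trends over time, assuming that changes occur similarly across all sites".
- **Reach of that model**: outside knowledge, it is carried only to continuous secondary scales: "Differences in the continuous outcome scales by intervention group will be assessed via the linear mixed model described previously".
- **Definition of the groups**: the opening paragraph compares "those enrolled during the control period and those enrolled during the intervention period".

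The SAP gives no number of sites, steps or patients, no expected tau and no expected trend.

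**The concern.** In a stepped wedge, sites move from control to intervention as the trial proceeds, so a participant's group depends on site and enrolment date together. Control participants are on average early and intervention participants late. If the link between values and choice changes over calendar time for reasons unrelated to the decision aid, a single tau per group attributes part of that change to the intervention, or hides a real effect behind it.

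The SAP already treats calendar trend as worth removing for knowledge and gives no reason to exempt concordance. It states the estimator, contrast and interval for this endpoint, so the point concerns the analysis as written and not a detail left to the protocol. At stake is whether a co-primary result can be read as an effect of the decision aid.

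**Working it through.** There is no SAP figure to reproduce. Every design input below is an assumption.

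**1. Share of a trend that enters the contrast.** Assume S sites, one crossing per step, S+1 periods numbered 0 to S, equal enrolment and a linear trend. Period t has t intervention sites.

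- Mean intervention period, as a fraction of the trial: (Σt² / Σt) / S = (2S+1)/(3S).
- Mean control period, by symmetry: (S−1)/(3S).
- Difference: (S+2)/(3S).

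S = 3: 5/9 = 56%. S = 4: 6/12 = 50%. S = 6: 8/18 = 44% (means at 72% and 28% of the trial). S = 12: 14/36 = 39%.

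**2. Effect on the tau difference.** Simulated trials with no intervention effect: 6 sites, 7 periods, 6 patients per site and period (252 patients), score 1–10, log-odds slope of choice on values 0.35 per point, no site variation, patients resampled within group.

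| Change over the trial | False tau difference | Interval excludes 0 |
|---|---|---|
| None | about 0 | about 5% |
| Slope +25% | 0.03 | 7% |
| Slope +50% | 0.05 | 10–12% |
| Slope +100% | 0.09 | 21–24% |
| Declining at the mean score falls from 50% to 15% | −0.035 | 8% |
| Declining at the mean score falls from 50% to 10% | −0.058 | 10–11% |

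Ranges cover repeated runs. With values skewed towards score 1, the slope rows give 6%, 9% and 17%, and the uptake rows 5% and 6%, against 5.7% with no drift.

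A different generating model on the same layout, with a latent values-choice correlation rising from 0.2 to 0.4, 0.1 to 0.5 or 0.0 to 0.6, gives 9.8%, 19.5% and 36%.

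**3. Sample size.** At a 50% slope rise the false difference stays at 0.05–0.06 for 252, 504 and 1,008 patients, while exclusion of zero rises from 12% to 15% to 28%.

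**4. Period-stratified tau.** Taking the tau difference within each period and combining brings the mean false difference to between −0.01 and 0.00, with exclusion of 4.4–6.0%, in the 252-patient scenarios without site variation.

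**5. Price in precision.** The SD of the estimate is 0.133 stratified against 0.090 pooled: ratio 0.133/0.090 = 1.48, variance ratio 2.2. Much of this comes from the layout. With weights n1·n0/(n1+n0), the five periods containing both groups contribute 5+8+9+8+5 = 35, against 126·126/252 = 63 for the pooled contrast. That alone gives √(63/35) = 1.34.

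**6. Site variation** (SD of site intercept / SD of site slope).

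| Analysis | SD 0.5 / 0.1 | SD 1.0 / 0.2 |
|---|---|---|
| Pooled tau | 6.8–7.4% | 9–10% |
| Period-stratified tau | 6.6–8% | 10–13% |
| Logistic model, random site intercept | 5.8% | 15% |

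Entries are the share of null trials with a falsely significant result. The logistic figures rest on 400 trials each, with a Monte Carlo standard error of about 1.3 points.

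**The case against.** **The two analyses do not contradict each other.** Period indicators in the knowledge model remove a trend in a mean. A uniform shift in a mean does not by itself move a correlation. Concordance needs a trend in the strength of the association, or a large shift in the choice split, and nothing in the SAP points to either. This stands. The inconsistency is one of caution, not of logic.

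**The harm is small at modest drift.** At an SD of 0.090, the difference detectable with 80% power is about 2.8 × 0.090 = 0.25, well above a false 0.03–0.05. This also stands for a trial of about 252 patients, but the SAP gives no size, and the bias persists as the interval narrows.

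**Adjustment can make the estimate worse.** At 252 patients the root-mean-square error, stratified against pooled, is 0.129 against 0.091 at a 25% slope rise, 0.123 against 0.099 at 50%, and 0.114 against 0.116 at 100%. At 1,008 patients it is 0.061 against 0.052, 0.054 against 0.069, and 0.051 against 0.095. The trade-off is real, and one could argue for a period-adjusted sensitivity analysis only. However, a confirmatory contrast between groups that differ in calendar time needs protection against a trend that the design builds into the comparison. Adjusting for period in a stepped wedge is standard practice, and this SAP follows it for the other co-primary.

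**Stratifying by period does not deal with site.** This stands. Step 6 shows it does no better than pooled tau under site variation.

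**Site-level resampling may be intended.** The resampling unit is not stated. Resampling sites would change the interval's width but leave the period bias in the estimate.

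**Conclusion.** The concern holds for period. As written, the concordance co-primary lets a share of any calendar trend in the values-choice association into the intervention contrast: 39–56% of a linear trend in balanced layouts of 3 to 12 steps. A larger trial does not reduce that share. At an assumed 252 patients, false exclusion of zero is 7–12% for a 25–50% slope rise and about 21–24% if the slope doubles.

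A reader might infer more than the document supports:

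- *That the concordance result is biased in this trial.* The SAP shows no trend, and all sizes rest on assumed designs. Confidence is high for the gap in the text, not for material bias.
- *That a trend in LVAD uptake alone is a serious second route.* It moves tau somewhat in the symmetric scenario but matters little when values are skewed.
- *That period stratification gives a valid interval outright.* It does so only if site variation is small.
- *That most periods contain both groups, so adjustment is always easy.* The SAP gives no layout. With three steps of the kind assumed here, only two of four periods do.

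This should be fixed before analysis.

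**What to change.** Make the co-primary concordance contrast period-adjusted, in one of two ways:

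1. Keep tau. Take the tau difference within each period containing both groups, combine with weights n1·n0/(n1+n0), and bootstrap within period and group.
2. Fit a logistic model of choice with values score, intervention, values × intervention, categorical period, values × period and a site effect, and test values × intervention.

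In either case, state how site enters the interval. Option 1 removes period bias only. In option 2 a site intercept alone is not safe under strong site variation, and site-specific values slopes are feasible only if the number of sites supports them. Keep pooled tau as a description and treat 6-month concordance the same way.

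**Cost.** SAP wording, and a standard error about 1.4–1.5 times larger (variance about 2.2-fold for stratified tau). In a small trial the estimate is no closer to the truth unless drift is large. Tau can be undefined in sparse periods: about 1% of periods in the 6-site layout, up to 8% if few patients decline, and about 12% with 12 sites and 2 patients per site and period. Adjacent periods may therefore need merging by a rule set in advance. Option 2 changes the measure from tau to a log-odds slope interaction.

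The number of bootstrap draws, the resampling unit and the handling of patient-caregiver pairs are separate clarifications.

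### Categorical secondary scales are tested by a plain chi-square that ignores site and stepped-wedge period, while continuous scales are adjusted for both

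*SAP*

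**What the plan says.** All of this is in the SAP, under the heading Extended Statistical Analysis Plan.

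- **Categorical secondary scales** (analysis paragraph after the list of secondary outcomes): "Significance for differences by intervention group at specified time points for the categorical outcome scales will be determined using Chi-square tests". No site, period or covariate term is named.
- **Continuous secondary scales** (next sentence): "Differences in the continuous outcome scales by intervention group will be assessed via the linear mixed model described previously".
- **That model** (Knowledge): it "included a random effect for site and fixed effect indicators of intervention group and stepped wedge time period". The stated reason is: "This model adjusts for trends over time, assuming that changes occur similarly across all sites". The SAP also "will include covariates that are imbalanced by group in this linear mixed model", so covariate adjustment is likewise confined to the mixed model.
- **Design and groups**: the SAP says "we will fit a linear mixed model proposed for the analysis of stepped wedge designs", and its opening paragraph compares baseline characteristics "between those enrolled during the control period and those enrolled during the intervention period".

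The SAP does not list which scales are categorical. The likeliest is the patients' decision-role measure, assessed "using the validated Control Preferences Scale and their actual control participation". A dichotomised PHQ-2 or single acceptability items are possible.

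**The concern.** The SAP recognises that this design needs adjustment for calendar time, then leaves the adjustment out for one class of outcomes without giving a reason. Two problems follow.

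1. **Bias from trend.** Intervention status is tied to calendar period. Any drift in the outcome over the study, such as changing case mix or counselling practice, enters the crude difference. It can push in either direction.
2. **Wrong variance from site.** Sites that cross late supply mostly control patients and sites that cross early supply mostly intervention patients. Differences between sites therefore add noise to the group comparison that the chi-square does not count.

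For the affected scales, a significant result could reflect trend or site mix, and an opposing trend could mask a real effect. Two secondary scales could also lead to different conclusions only because one was coded in categories and the other as a score.

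**Working it through.** **No figure to reproduce.** The SAP gives no number of sites or periods, sample size, intraclass correlation (ICC), base rate or test level for these outcomes. Everything below is an illustration on assumed inputs.

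**Assumed layout.** 6 sites, 7 periods (0 to 6), one site crossing at each step, 6 patients per site-period: 6 × 7 × 6 = 252 patients. Binary outcome, 40% base rate, two-sided 5% test. Drift is linear on the logit and quoted as the total change. ICC is on the logit scale.

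**Step 1: confounding by design.** Site *i* has *i* control periods and 7 − *i* intervention periods, so each group has 21 cells (126 patients).

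- Mean period, control: (0+1+3+6+10+15)/21 = 35/21 = 1.67. Intervention: (126 − 35)/21 = 4.33.
- Share from the last two sites to cross: control (5+6)/21 = 52%; intervention (2+1)/21 = 14%.

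**Step 2: drift alone, no true effect.** The groups differ by 4.33 − 1.67 = 2.67 periods out of 6. A total drift of 0.6 logit (40% to 55%) shifts the groups apart by 0.6 × 2.67/6 = 0.267 logit. Multiplied by p(1−p) ≈ 0.249, that is about 6.6 percentage points. The standard error is √(2 × 0.249/126) = 6.3 points, so the expected z is 1.05. Rejection is P(Z > 1.96 − 1.05) + P(Z < −1.96 − 1.05) ≈ 18%.

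**Step 3: site variation alone, no true effect.** The difference between a site's shares of the two groups is (7 − 2*i*)/21. The squares sum to 70/441 = 0.159. With 126 per group, the variance of the crude difference is inflated by about 1 + (0.159 × 126/2 − 1)ρ = 1 + 9ρ, where ρ is the ICC on the probability scale. A logit ICC of 0.05 means a site variance of 0.05 × (π²/3)/0.95 = 0.173 and ρ ≈ 0.173 × 0.24 = 0.042. The inflation is 1.37, and rejection is P(|Z| > 1.96/√1.37) ≈ 9%.

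**Step 4: simulation of the same layout.** Ranges are across independent runs of 4,000 to 40,000 trials per scenario.

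| No true effect | Chi-square rejects |
|---|---|
| No drift, ICC 0 | 4.5–4.9% |
| ICC 0.01–0.02, no drift | about 6% |
| ICC 0.05, no drift | 8.8–9.3% |
| ICC 0.10, no drift | 12.9–14.1% |
| Drift 0.3 (40% to 47%), ICC 0 | 8.0–8.2% (false difference 3.3 points) |
| Drift 0.6 (40% to 55%), ICC 0 | 18.0–18.9% (6.6–6.7 points) |
| Drift 1.2 (40% to 69%, a strong trend), ICC 0 | 53.9–54.8% (13.0–13.1 points) |

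With a true 15-point effect at ICC 0.05:

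| Drift | Mean crude difference | Rejection |
|---|---|---|
| 0 | 14.4 points | 62% |
| +0.6 | 20.4 points | not quoted |
| −0.6 | 7.9 points | about 28% |
| −1.2 | 1.4 points | 9% |

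**Step 5: other layouts.** A separate simulation used 4 to 10 sites, 4 to 7 periods, about 240 to 300 patients, a 50% rate, and equal or unequal cell sizes. Chi-square rejection was 4.3–5.6% with neither trend nor site effect. It was 11–14% for a 10-point trend alone and 7–12% for ICC 0.05 alone.

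**Step 6: with site and period in the model.** In the layout of step 1, logistic regression with site and period indicators rejected 5.0–6.4% across 12 null scenarios (ICC 0 to 0.10, drift 0 to 1.2). A random-intercept logistic model rejected 5.3–7.3% uncorrected and 3.9–6.3% with a t reference on 29 degrees of freedom.

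**The case against.** **The size is unknown, and small departures matter little.** This stands. In the assumed layout a total drift of 0.1 logit gives about 5.1% rejection and an ICC of 0.01 under 6%. If every site had the same control-to-intervention split, site variation alone would tend to make the test conservative. The percentages show how the error grows; they do not predict this trial.

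**The scope is narrow.** Only secondary outcomes are involved, the affected scales are not named, and most listed measures may be scored as continuous and so already go to the mixed model. The SAP also ties scoring to the published method for each instrument, which may settle part of the coding. This limits the severity. It does not supply adjustment for whichever scales end up as categories.

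**The protocol may cover it.** It would not change the point. The SAP names the test that determines significance, and no detail of sites or sample size would make an unadjusted chi-square account for period.

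**The adjusted model costs power and may fail on sparse categories.** Both are true, and only binary outcomes were simulated. The crude test's apparent power at ICC 0.05, however, comes from a test that rejects about 9% under the null.

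**Conclusion.** The concern holds. The SAP sets an inferential rule for the categorical secondary scales that omits the site and period adjustment it gives as the reason for its own model. Nothing else in the document supplies that adjustment. The contrast is in the text and needs no assumption.

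The size does need assumptions. Under the layouts tried, moderate trend or site variation takes a nominal 5% test to roughly 7–19%, a strong trend takes it above 50%, and an opposing trend can more than halve the chance of detecting a real effect. With neither, the test is close to nominal. This should be corrected, but it does not reach the co-primary endpoints, and the number of scales affected cannot be determined from the SAP.

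**What to change.** 1. List the scales, and the time points, that will be analysed as categorical.
2. Replace their chi-square tests with the model that matches the outcome: logistic for binary, ordinal for ordered and multinomial for unordered categories. Use fixed effects for intervention and stepped-wedge period, a site effect, and a small-sample correction. GEE with such a correction is an alternative. Choose one in advance for each scale.
3. Add the same imbalanced covariates that enter the linear mixed model, so both types of scale are treated alike.
4. Keep raw counts and percentages by group as description.
5. Fix in advance when categories count as too sparse to model. In that case collapse them by a stated rule, or report the chi-square comparison descriptively with no significance claim.

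**Cost.** SAP wording and a few more model fits on data already collected. The loss of precision is material. In the assumed layout, for a 15-point effect at ICC 0.05 with no trend, power is about 60–62% crude. It is 27% with fixed site and period terms, and 31–34% with a random site effect. The lower figures are what the design can support once site and period are accounted for.

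### The SAP commits to missing at random, but the Kendall's tau co-primary and the chi-square tests have no step that delivers it and, as written, default to complete records

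*SAP*

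**What the plan says.** All the relevant text is in the SAP's single section, Extended Statistical Analysis Plan.

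- **Missing data** (short paragraph after the secondary outcomes): "Missing data will be characterized at each time point", followed by "Analysis will account for missing data and will relax the missing data assumptions to missing at random conditional on observed data". No technique, conditioning variables or list of covered analyses is given.
- **Concordance co-primary** (Values-Choice Concordance): "Concordance between 1-month value score and patient/caregiver-reported treatment choice at 1-month is the other co-primary endpoint". Both variables come from the 1-month assessment. The secondary version pairs the same 1-month score with implantation by 6 months, taken from the medical record.
- **Estimator for concordance**: "we will calculate the Kendall's tau correlation coefficient between the stated values score at 1 month and each of the treatment outcomes". The group difference in tau is then taken, and for its interval "we will perform 500 bootstrap samples", using the 2.5 and 97.5 percentiles.
- **Categorical secondary outcomes**: "Significance for differences by intervention group at specified time points for the categorical outcome scales will be determined using Chi-square tests".
- **Knowledge co-primary and continuous secondary scales**: a linear mixed model with a site random effect and terms for group and stepped-wedge period. It handles repeated measures within subject.

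**The concern.** The missing-data sentence is general, and its own verb concedes that a stronger assumption applies unless something is done. For two of the three kinds of analysis, the SAP describes nothing that does it.

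Kendall's tau can be computed only for a person with both a values score and a choice. The two come from the same 1-month contact, so they are likely to be missing together. Suppose non-response depends on something related to values and choice, and does so differently in the control and intervention periods. Complete-pair tau can then differ between groups when the true difference is zero. Bootstrapping those pairs does not help: each resample carries the same selection, so the interval sits around the biased value. Tau also has no site, period or covariate term.

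The chi-square tests share the problem and, in a stepped-wedge design, also ignore site and period. What is at stake is one of the two co-primary endpoints and all the categorical secondary outcomes.

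**Working it through.** The SAP states no missingness rate, sample size or power that bears on this point, so there is no figure of its own to reproduce. The check has two parts.

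**1. Promise against method**

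| Analysis | Method stated | Step that conditions on observed data |
|---|---|---|
| Knowledge (co-primary) | Linear mixed model, repeated measures | Yes, through the likelihood, given what is in the model |
| Concordance with 1-month choice (co-primary) | Kendall's tau by group, percentile bootstrap | None |
| Concordance with 6-month implant status | Same | None (implant status comes from the record, but the values score still needs the 1-month response) |
| Continuous secondary scales | Same linear mixed model | Yes, as for knowledge |
| Categorical secondary scales | Chi-square at each time point | None |

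**2. Illustration of size**

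Every input here is assumed; none comes from the SAP.

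*Set-up A.* There are 1,000,000 patients per group and the same true association in both.
- Baseline variable: z0 ~ N(0,1), observed for everyone.
- One-month latent value: z1 = 0.7·z0 + √(1 − 0.49)·e, with e ~ N(0,1).
- Values score: V = round(5.5 + 2.5·z1 − 1.5), clipped to 1–10.
- Choice of LVAD: P = 1/(1 + exp(−(0.3 − 0.4(V − 5)))).
- Intervention group: P(missing) = 1/(1 + exp(−(a + 2·z0))), with a set to give the overall rate. Control group: same rate, at random.
- Weighted comparator: each observed pair weighted by 1/P(observed), using the known probabilities.

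True tau-b is about −0.334 in both groups, so the true difference is 0.

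| Missing | Complete-pair tau, intervention | Complete-pair difference | Weighted difference |
|---|---|---|---|
| 10% | −0.318 | 0.015 | 0.001 |
| 20% | −0.308 | 0.025 | −0.001 |
| 30% | −0.299 | 0.035 | 0.000 |
| 40% | −0.293 | 0.042 | 0.000 |

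With missingness completely at random, or dependent on group alone (control losing half the intervention rate), the complete-pair difference stayed within 0.002 of zero.

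*Set-up B.* There are 60,000 patients per group, half of them sicker with weak concordance, and tau is 0.34 in both groups (coded positive). With 30% of sicker controls missing against 15–20% of sicker intervention patients, the difference is about −0.02. With 50% against 15–20%, it is about −0.05.

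The sign reflects the coding and the assumed mechanism and carries no information about this trial. In absolute value the two set-ups together give roughly 0.02 to 0.05.

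*Against sampling error.* In a further simulation similar to B (strata tau 0.16 and 0.50, no loss among less-sick patients), the differences were −0.015 and −0.037. At an assumed 100 to 200 per group, the standard error of the tau difference was 0.10 to 0.07. For a bias of 0.02 to 0.05 the ratio runs from 0.02/0.10 = 0.2 to 0.05/0.07 ≈ 0.7 standard errors.

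**The case against.** A reader might infer that the SAP plans a complete-pair analysis, so that the concordance co-primary depends on data being missing completely at random. The documents do not support that, for three reasons.

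- The SAP nowhere says that tau is confined to observed pairs, and nowhere excludes imputing or weighting first. Its missing-data sentence is not limited to the mixed model.
- Tau is a statistic and chi-square a test; neither is a missing-data method. Either can follow imputation or weighting, and the weighted tau above returned to within 0.001 of zero.
- Even complete pairs do not need missingness completely at random. If missingness depends on group alone, tau within each group remains valid.

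It is also fair to say that the mechanism and its size come from assumptions. The upper figure of 0.05 needs half of the sicker controls to be missing, and at plausible group sizes the bias is smaller than the sampling error.

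Finally, a mixed logistic or ordinal model at a single time point still drops anyone without that outcome. It mainly addresses clustering and time trend.

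All of this stands, and it limits the point to a promise with no method behind it. It does not remove the point. If imputation or weighting is intended, it is unspecified and could be chosen after the data are seen. If it is not intended, the promise is not kept for tau and chi-square. Both cases call for the same amendment.

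**Conclusion.** The point holds as a mismatch between a stated assumption and the stated methods. Only the linear mixed model can deliver missing at random. Tau and the chi-square tests, run as written, default to complete records and are valid only if missingness within each group is unrelated to the outcomes. That tau is a co-primary makes this worth correcting.

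The size and direction of any bias in this trial cannot be judged from the SAP. The range of about 0.02 to 0.05 depends on the assumed missingness rates, the assumed link between the driver of non-response and concordance, and a difference in that pattern between groups. The weighted result shows that the bias can be removed when the driver is observed and the response model is right. It says nothing about missingness that depends on unobserved data.

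**What to change.** **Concordance (tau).** Within each bootstrap resample, impute the 1-month values score and choice jointly, separately by group, and then compute tau. Re-estimating inverse-probability-of-response weights in each resample is an alternative. As predictors use baseline 1 and baseline 2 responses, site, period and 6-month implant status; the last comes from record review and does not depend on survey response. Name the variables and the analyses covered. Report deaths before 1 month by group. Keep complete-pair tau as a sensitivity analysis.

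**Categorical secondary outcomes.** Replace chi-square with a mixed logistic or ordinal model with a site random effect and period, matching the model for the continuous scales. On its own this relaxes the missingness assumption only to site, period and group. To support the missing-at-random claim, apply the same imputation or add baseline covariates.

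**Cost.** SAP wording and more programming, with no new data. The downside is reliance on an imputation or weighting model. If both 1-month items are usually missing together, the benefit depends on how well the earlier responses and implant status predict them.
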